11.0 Study Timelines

11.1 Describe the anticipated duration needed to enroll all study subjects.

Response:

12 months

11.2 Describe the duration of an individual subject's participation in the study. Include length of study visits, and overall study follow-up time.

Response:

The overall subject's participation time is 12 - 24 months

After the 2 hours screening visit, eligible patients will be scheduled for 3 visits including the two visits of surgical therapy, followed by one day and 2 weeks follow-up visits and 6 weeks, 3, 6, 12, 18, and 24 months evaluations visits for a total of 15 visits distributed over 12-24 months. Each appointment is expected to be 30 minutes to 3 hours except surgical therapy visit is 3-4 hours.

11.3 Describe the estimated duration for the investigators to complete this study (i.e. all data is collected and all analyses have been completed).

Response:

24 months

12.0 Setting

12.1 Describe all facilities/sites where you will be conducting research procedures. Include a description of the security and privacy of the facilities (e.g. locked facility, limited access, privacy barriers). Facility, department, and type of room are relevant. Do not abbreviate facility names.

NOTE: Examples of acceptable response may be: "A classroom setting in the Department of Psychology equipped with a computer with relevant survey administration software," "The angiogram suite at Buffalo General Medical Center, a fully accredited tertiary care institution within New York State with badge access," or, "Community Center meeting hall."

Response:

The periodontal clinics at the university at Buffalo/ School of Dental Medicine. The dental school has card access for personnel, with security cameras in the hallways leading to/from clinics. Clinics are fully locked after working hours with no access to any staff/personnel. The subjects' data will be stored at [name] office locked cabinets in the Department of Periodontics and Endodontics at the university at Buffalo which is a locked office with access to only him and his research assistant.

12.2 For research conducted outside of UB and its affiliates, describe:

- Site-specific regulations or customs affecting the research
- Local scientific and ethical review structure

NOTE: This question is referring to UB affiliated research taking place outside UB, i.e. research conducted in the community, school-based research, international research, etc. It is not referring to multi-site research. UB affiliated institutions include Kaleida Health, ECMC, and Roswell Park Cancer Institute.

Response:

N/A: This study is not conducted outside of UB or its affiliates.

13.0 Community-Based Participatory Research

13.1 Describe involvement of the community in the design and conduct of the research.

NOTE: Community-Based Participatory Research (CBPR) is a collaborative approach to research that equitably involves all partners in the research process and recognizes the unique strengths that each brings. CBPR begins with a research topic of importance to the community, has the aim of combining knowledge with action and achieving social change to improve health outcomes and eliminate health disparities.

Response:

N/A: This study does not utilize CBPR.

13.2 Describe the composition and involvement of a community advisory board.

Response:

N/A: This study does not have a community advisory board.

14.0 Resources and Qualifications

14.1 Describe the qualifications (e.g., education, training, experience, expertise, or certifications) of the Principal Investigator **and** staff to perform the

research. When applicable describe their knowledge of the local study sites, culture, and society. Provide enough information to convince the IRB that you have qualified staff for the proposed research.

NOTE: If you specify a person by name, a change to that person will require prior approval by the IRB. If you specify a person by role (e.g., coordinator, research assistant, co-investigator, or pharmacist), a change to that person will not usually require prior approval by the IRB, provided that the person meets the qualifications described to fulfill their roles.

Response:

Principle investigator is a diplomate of the American Board of Periodontology, a clinical assistant professor, and the director of the post-graduate periodontal program at the university at Buffalo with years of experience in teaching and research, where he performed multiple retrospective and prospective clinical studies other than reviews and non-clinical studies. The co-investigator is an external study team member whom might be involved in supervising the Pinhole surgical procedure, clinical examiner and research coordinator will be Periodontists and/or periodontal resident. His staff will consist of an experienced dental assistant and hygienists that are well trained to conduct clinical research with experience in patient's privacy maintenance and following IRB guidelines. Lastly, the consulting statistician and epidemiologist is an external team member whom will be overlooking the study raw data without any identifiable patient information.

Describe other resources available to conduct the research.

14.2 Describe the time and effort that the Principal Investigator and research staff will devote to conducting and completing the research.

NOTE: Examples include the percentage of Full Time Equivalent (FTE), hours per week. The question will elicit whether there are appropriate resources to conduct the research.

Response:

0.2 FTE

14.3 Describe the availability of medical or psychological resources that subjects might need as a result of anticipated consequences of the human research, if applicable.

NOTE: One example includes: on-call availability of a counselor or psychologist for a study that screens subjects for depression.

Response:

The patients will be provided with the phone number of the research assistant, whom has direct contact with the surgeon and principle investigators, to call in case of dental adverse events or emergencies, and patients can be seen on emergency basis any day of the week if needed. In case of medical emergency, patients will be instructed to call 911. And in case of medical emergencies during the dental visit or treatment, a code team is always available during working

hours, which are trained in medical emergencies and patient's condition stabilization.

14.4 Describe your process to ensure that all persons assisting with the research are adequately informed about the protocol, the research procedures, and their duties and functions.

Response:

All persons assisting will be gathered in a meeting at the beginning of the study to explain to them the protocol of the study, copies of the protocol will be given to them and all questions will be answered then responsibilities and duties will be assigned to each member. Also, The principle investigator and research assistant will be available, on the phone and email address, to answer any question or concern from the staff throughout the study. GCP principles will be closely adhered and the research staff will be trained accordingly.

15.0 Other Approvals

15.1 Describe any approvals that will be obtained prior to commencing the research (e.g., school, external site, funding agency, laboratory, radiation safety, or biosafety).

Response:

IRB approval, organization sponsor approval, funding agency approval.

N/A: This study does not require any other approvals.

16.0 Provisions to Protect the Privacy Interests of Subjects

16.1 Describe how you will protect subjects' privacy interests during the course of this research.

NOTE: Privacy refers to an individual's right to control access to him or herself. Privacy applies to the person. Confidentiality refers to how data collected about individuals for the research will be protected by the researcher from release. Confidentiality applies to the data.

Examples of appropriate responses include: "participant only meets with a study coordinator in a classroom setting where no one can overhear", or "the participant is reminded that they are free to refuse to answer any questions that they do not feel comfortable answering."

Response: The subjects will be interviewed and their information will be reviewed with them in the clinic that has closed doors with no other people other than the research staff around. Also, all subjects will be reminded that they have the right to refuse to answer any questions that they do not feel comfortable answering. And they can withdraw from the study at any time.

16.2 *Indicate how the research team is permitted to access any sources of information about the subjects.*

*NOTE: Examples of appropriate responses include: school permission for review of records, consent of the subject, HIPAA waiver. This question **does apply** to records reviews.*

Response:

HIPPA authorization and consent will be approved by the included subjects before the beginning of the study. The research staff will have access to the information provided by the patients.

17.0 Data Management and Analysis

17.1 *Describe the data analysis plan, including any statistical procedures. This section applies to both quantitative and qualitative analysis.*

Response: The main aim of this study is to assess the efficacy of the pinhole surgical technique in treating gingival recession compared to an established surgical treatment method. We therefore will focus in this clinical trial on one primary endpoint, namely recession depth. The change in recession depth during the study observation period will therefore be used for the calculation of sample size.

We previously have calculated the sample size based on parameter estimates gathered from published studies. We now have recalculated the sample size and used parameters estimates generated from 28 cases already treated in this clinical trial. This should give more accurate parameters to calculate the sample size needed. We also used the 80% power. Accordingly, we used the following assumptions to calculate the sample size:

Standard deviation in the group A: 0.91

Standard deviation in the group B: 0.95

Correlation: 0.46

Effect size (the difference in the reduction in recession depth between the test and control groups): 0.4 mm

Level of significance: 0.05

Power: 80%

Type of test: 2-sided

Based on these assumptions, the sample size is 48. In addition, we anticipate a drop out of 4 subjects. Hence, the total number of participants needed for this study is 52.

17.2 *If applicable, provide a power analysis.*

NOTE: This may not apply to certain types of studies, including chart/records reviews, survey studies, or observational studies. This question is asked to elicit whether the investigator has an adequate sample size to achieve the study objectives and justify a conclusion.

Response: Please see item 17.1

17.3 *Describe any procedures that will be used for quality control of collected data.*

Response:

Standardization of measurement and radiographs and assurance of intraoperator reproducibility will be performed.

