6.0 Inclusion and Exclusion Criteria

6.1 Describe the criteria that define who will be **included** in your final study sample.

NOTE: This may be done in bullet point fashion.

Response:

- 1- The patients should be above 18 years old.
- 2- The presence of Miller's class I or II gingival recession on at least two matching bilateral or contralateral gingival recession defects (≥ 2 mm).
- 3- Recession defect on maxillary incisors, maxillary and mandibular canines, or premolars.
- 4- Absence of a history of periodontal surgery at the involved sites in the last 12 months.

- 5- History of compliance with oral hygiene instructions and periodontal recall.
- 6- Sufficient palatal or tuberosity donor tissue thickness (> 2mm).

6.2 Describe the criteria that define who will be **excluded** from your final study sample.

NOTE: This may be done in bullet point fashion.

Response:

- 1- Patients with systemic illness known to affect the outcome of periodontal therapy, including diabetes, immune deficiencies, etc.
- 2- Pregnant and lactating women
- 3- History of allergic reactions to drugs or materials used in the surgery including collagen.
- 4- Current use of any form of tobacco.

6.3 Indicate specifically whether you will include any of the following special populations in your study using the checkboxes below.

NOTE: Members of special populations may not be targeted for enrollment in your study unless you indicate this in your inclusion criteria.

Response: none

- Adults unable to consent
- Individuals who are not yet adults (infants, children, teenagers)
- Pregnant women
- Prisoners

6.4 Indicate whether you will include non-English speaking individuals in your study. **Provide justification if you will exclude non-English speaking individuals.**

*In order to meet one of the primary ethical principles of equitable selection of subjects, non-English speaking individuals may **not** be routinely excluded from research as a matter of convenience.*

In cases where the research is of therapeutic intent or is designed to investigate areas that would necessarily require certain populations who may not speak English, the researcher is required to make efforts to recruit and include non-English speaking individuals. However, there are studies in which it would be reasonable to limit subjects to those who speak English. Some examples include pilot studies, small unfunded studies with validated instruments not available in other languages, studies with

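### Section 17.1 defines and sizes the technique effect as an unadjusted within-patient difference in recession-depth reduction; using the within-pair baseline difference as a covariate could sharpen it with data already collected

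*Protocol*

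**What the plan says.** Section 17.1 of the protocol answers the request for a data analysis plan. It narrows the trial to a single endpoint: "We therefore will focus in this clinical trial on one primary endpoint, namely recession depth". It then states "The change in recession depth during the study observation period will therefore be used for the calculation of sample size" and gives the target as "Effect size (the difference in the reduction in recession depth between the test and control groups): 0.4 mm". The other inputs are "Standard deviation in the group A: 0.91", "Standard deviation in the group B: 0.95", "Correlation: 0.46" and "Level of significance: 0.05", two-sided, with 80% power. They come from 28 cases already treated in this trial. The result is 48 subjects, plus 4 for dropout, making 52. No test or model is named for the primary comparison. The only test named in the protocol, a paired t-test in section 19.8, is for safety data.

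On the pairs, section 6.1 asks for Miller class I or II recession on "at least two matching bilateral or contralateral gingival recession defects (≥ 2 mm"), on listed tooth types. It gives no tolerance for the difference in depth between the two sites, and section 10.1 repeats the matching requirement without defining it.

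Section 10.1 records recession depth at baseline at each study site. It defines percentage root coverage as the reduction divided by preoperative depth, and complete root coverage as 100%.

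**The concern.** The reduction at a site is tied to its starting depth. Under the definitions in section 10.1, complete coverage means that the reduction equals the baseline depth. If depth is scored no lower than zero, the reduction cannot exceed baseline. As an illustration (not trial data), take a 2 mm site and a 4 mm site, both fully covered. They differ by 2 mm in reduction although both techniques succeeded completely. Percentage root coverage scales this away; the effect measure in 17.1 does not.

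Without a depth tolerance, pairs of unequal depth can enter. The part of the baseline difference that predicts the difference in reduction then sits in the error of a simple paired comparison. With about 48 pairs, that means a wider interval for the technique effect than the data could support. Interval width matters both for the two-sided test used for sizing and for the non-inferiority hypothesis in section 1.2.

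**Working it through.** **Inputs.** From section 17.1: SDs 0.91 and 0.95 mm, correlation 0.46, difference 0.4 mm, two-sided alpha 0.05, 48 pairs. The SDs and correlation are taken to be those of the change in depth, as the effect-size wording implies and the reproduction below supports.

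**Step 1: reproduce the plan's figure.**

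- SD of the within-patient difference = √(0.91² + 0.95² − 2 × 0.46 × 0.91 × 0.95) = √0.9353 = 0.967 mm.
- Standard error at 48 pairs = 0.967/√48 = 0.1396 mm; noncentrality = 0.4/0.1396 = 2.87.
- Paired t-test, noncentral t: power 80.1% at 48 pairs and 79.3% at 47.

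So 48 is exactly the size for an unadjusted paired t-test on change. The 95% CI half-width is 2.012 × 0.1396 = 0.281 mm.

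**Step 2: add the within-pair baseline difference.** Let ρ be the correlation, across patients, between the difference in baseline depth and the difference in reduction (PST minus CTG for both). Residual SD = 0.967 × √(1 − ρ²), with 46 degrees of freedom instead of 47. The protocol does not give ρ, so the values below are assumed.

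| ρ (assumed) | Residual SD, mm | Power at 48 pairs | CI half-width, mm |
|---|---|---|---|
| Unadjusted | 0.967 | 80.1% | 0.281 |
| 0.1 | 0.962 | 80.5% | 0.280 |
| 0.2 | 0.948 | 81.7% | 0.275 |
| 0.3 | 0.923 | 83.7% | 0.268 |
| 0.5 | 0.838 | 90.0% | 0.243 |
| 0.7 | 0.691 | 97.5% | 0.201 |

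**Step 3: what ρ means in millimetres.** ρ = slope × SD of the within-pair baseline difference / 0.967. With an assumed slope of 0.7:

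- SD 0.25 mm: ρ = 0.18, power 81.4%.
- SD 0.5 mm: ρ = 0.36, power 85.3%.
- SD 0.75 mm: ρ = 0.54, power 91.6%.

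**Step 4: the price of adjusting.** The table takes the mean baseline difference between techniques as zero. Randomisation makes it zero only on average. Estimating the slope multiplies the variance of the intercept by about 1 + 1/(48 − 3) = 46/45 on average, if baseline differences are roughly normal. That is worth about one pair (48 × 45/46 ≈ 47), so with ρ = 0 power would be about 79.3%. Break-even is where (1 − ρ²) × 46/45 = 1, that is ρ = √(1/46) ≈ 0.15. Below that, adjustment costs a trace of precision; above it, adjustment gains.

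**The case against.** The strongest reply is that 17.1 does not commit to an unadjusted analysis. The sentence on change concerns sample size only, and covariates are commonly left to a statistical analysis plan, which is not shown here. Sizing on the unadjusted variance and then adjusting is ordinary, conservative practice. All of this stands. A reader might infer that the protocol fixes a raw paired comparison as its primary analysis, but the text does not say so.

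A reader might also infer that the trial is underpowered or the estimate biased. Neither follows. The variance inputs come from cases treated in this trial, so whatever baseline mismatch occurred in those cases is already inside the 0.967 mm, and 48 reproduces. Technique is randomised within the patient, so chance imbalance in baseline is sampling error that the interval already covers.

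Finally, the size of the gain is not shown. The protocol gives neither ρ nor the spread of baseline differences, and pairs chosen as matching may be close in practice. That also stands, and it rules out reading the higher rows of the table as a demonstrated loss.

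What survives is narrower. Section 17.1 states the effect without reference to baseline, section 6.1 sets no depth tolerance, and the covariate is already measured. The correlation of 0.46 leaves the SD of the paired difference (0.967 mm) no smaller than either single-site SD, so there is within-pair variation to explain. How much of it is baseline depth is unknown.

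**Conclusion.** The point holds as a precision improvement, not as an error. The effect in 17.1 is defined and sized as an unadjusted within-patient difference in reduction, and nothing in the eligibility rule limits the baseline difference that feeds its variance. The stated 48 is right under its own assumptions.

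The gain in power at 48 pairs runs from nothing useful (ρ up to about 0.2, at most 81.7%) through 84–90% (ρ of 0.3 to 0.5) to 97.5% (ρ of 0.7). The half-width falls from 0.281 mm to between 0.280 and 0.201 mm over ρ of 0.1 to 0.7. If ρ is near zero, the expected cost is about one pair's worth of information. These figures rest on assumed values of ρ, a roughly linear relation, and the 17.1 SDs and correlation being those of the change.

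**What to change.** Add to section 17.1 that the primary estimate is the intercept from regressing the within-patient difference in recession-depth reduction (PST minus CTG) on the within-patient difference in baseline recession depth, that is, the technique effect at equal baseline depth. If the statistical analysis plan already says this, 17.1 need only refer to it.

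If a mixed model is preferred, include both the subject-mean baseline and each site's deviation from it. A random-intercept model with site baseline alone mixes between-patient and within-patient slopes and is not equivalent to the difference regression.

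Keep 48/52 as the conservative unadjusted size. The 28 cases already treated can be used to estimate ρ (assuming each case is a patient with both sites treated), which would show whether the gain is worth reporting. The model itself should be fixed in advance and not chosen on that estimate.

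The cost is a sentence or two and one degree of freedom, with no new data and no change to visits or recruitment.

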18.0 Confidentiality

A. Confidentiality of Study Data

*Describe the local procedures for maintenance of confidentiality of **study data and any records that will be reviewed for data collection.***

18.1 A. *Where and how will all data and records be stored? Include information about: password protection, encryption, physical controls, authorization of access, and separation of identifiers and data, as applicable. Include physical (e.g. paper) **and** electronic files.*

Response:

All charts, data and materials for the study are held with the principle investigator, and are kept together in a file for each individual subject, while electronic data will be kept on a password protected disc, all materials are stored in a locked cabinet and access is limited to the principal investigator, and the research assistant. A password locked computer of the University that is further secured by a personal account is used for data analysis. All the data related to the results will be retained for 5 years after the completion of the study for long-term follow-up if needed. GCP (by ISO14155) principles will be followed in close adherence. Patient information will be stored under a code assigned for each patient only and no names will be stored to protect patient's confidentiality. Medical and dental history information will be saved until the 12 months follow-up is completed, as they are important in the clinical management of patients during the course of the study, and then will be safely discarded and not used in any data analysis.

18.2 A. *How long will the data be stored?*

Response:

5 years after the study is completed.

18.3 A. *Who will have access to the data?*

Response:

The principle investigator and his research assistant upon the approval of the principle investigator.

18.4 A. *Who is responsible for receipt or transmission of the data?*

Response:

Principle investigator and research assistant.

18.5 A. *How will the data be transported?*

Response:

Paper files and the electronic data disc are transported in large dark plastic boxes on the department's cart from/to the principle's investigator's office to/from the clinics where the study will be taking place by the principle investigator and/or research assistant. Electronic files will be accessed on the department and clinics computers that are password locked computers of the University that are further secured by a personal account user name and password.

B. Confidentiality of Study Specimens

*Describe the local procedures for maintenance of confidentiality of **study specimens**.*

N/A: No specimens will be collected or analyzed in this research.
(Skip to Section 19.0)

18.6 B. *Where and how will all specimens be stored? Include information about: physical controls, authorization of access, and labeling of specimens, as applicable.*

Response:

